Study Protocol

Title: Heart rate variability biofeedback training and emotion regulation

NCT number: NCT03458910

IRB approval date: 7/9/2018

Uploaded date: 2/28/2024

Research Objectives

The aim of the study is to examine the effects of two types of heart rate biofeedback training on emotional well-being and brain function. One group will be trained to increase heart rate variability (HRV) while the other group will be trained to decrease heart rate (HR) and HRV. We hypothesize that the increase-HRV group will have better emotional health in post-training compared with pre-training whereas the decrease-HR/HRV group will not show such improvements. Furthermore, we predict that the improvements will be smaller in older adults than in younger adults. In addition, we predict training-related changes in brain function. We hypothesize that the increase-HRV training groups will show a better ability to up- and down-regulate the amygdala during an emotion regulation task. We also predict that the HRV-increase training will lead to greater functional connectivity between the medial prefrontal cortex and the amygdala at rest.

Research Background

Heart rate variability (HRV) is defined as the variation in the time interval between heartbeats. High HRV is associated with a number of positive emotional health outcomes including lower depression and better emotion regulation (Geisler, Vennewald, Kubiak, & Weber, 2010; Patron, Messerotti Benvenuti, Favretto, Gasparotto, & Palomba, 2014). One technique to increase HRV is to manipulate breathing. Slow, paced-breathing (approximately 6 breaths/min) leads to a synchronized oscillation between respiration and heart rhythms and results in increasing heart rate variability via the interaction with the baroreflex system (Lehrer & Gevirtz, 2014). Previous research shows that repeating this technique over several weeks improved emotional health outcomes in non-clinical and clinical populations (Lehrer & Gevirtz, 2014). However, studies typically did not have an active comparison group and so it is not clear what the mechanisms of these changes were.

This technique is feasible for most people and they can learn it during a few training sessions. After the initial training, participants will take the HRV biofeedback device home - the device provides visual and/or auditory cues to the participant to control breathing and heart rhythms.

<http://doi.org/10.1016/j.autneu.2013.11.004>

Methods and Design

Week 1:

After telephone screening, a group of eligible participants in the same condition (HRV-increase or HR/HRV-decrease, up to 6 people) will be invited to visit the lab at the same time. 3-5 researchers will conduct this group session, which will take about 3 hours.

First, the researchers will explain the overview of the study and take any questions and concerns that they may have. This should take about 30 minutes.

Second, participants will individually fill out forms including a consent form, demographic information, and emotion questionnaires (e.g., CESD, STAI, relaxation and fatigue questionnaires). We will record their resting HRV for 5 minutes. These will take about 30 minutes.

Third, participants will be asked to complete two computer-based cognitive tasks (i.e., Stroop Task and Paced Auditory Serial Addition Test), while their heart rate, breathing, blood pressure, skin conductance and pupil size are being recorded using the lab biofeedback devices and the eye tracker. In the Stroop task, a color name (blue, green, or red) is presented on a computer monitor in a color that was either congruent or incongruent with the name. The participants' task is to press a key on the keypad corresponding to the color in which the word is presented rather than the color name. In the PASAT, the participant will be presented with single digit numbers and asked to sum the two most recent digits. The two tasks together take about 30 minutes.

Fourth, participants will be asked to complete cognitive and emotion tasks, which together take about 40 min: 1) Flanker Inhibitory Control and Attention Test, 2) List Sorting Working Memory Test, 3) Dimensional Change Card Sort Test, 4) Pattern Comparison Processing Speed Test, 5) Sustained Attention to Response Task (SART) and 6) emotion questions. The first four tests are part of the NIH Toolbox Cognition Battery. See "Watch Demo Video" in the below link for the description of each test: <http://www.healthmeasures.net/explore-measurement-systems/nih-toolbox/intro-to-nih-toolbox/cognition>

The fifth test, SART, measures sustained attention. In this task, participants will be asked to respond to target stimuli (e.g., "3") but inhibit responding to non-target stimuli (e.g., "8" or any other digits). https://www.youtube.com/watch?v=qCrB3I_ffpU

The emotion questions are part of the NIH Toolbox Emotion Measures:

<http://www.healthmeasures.net/explore-measurement-systems/nih-toolbox/intro-to-nih-toolbox/emotion>

Lastly, phlebotomists will collect blood samples up to 25 mL via venipuncture (<http://tendertouchmobilelabs.com>). Note that blood draw volume for blood donation in the US is 1 pint (~450 mL). Thus, 25 mL should be safe for our participants.

For the rest of Week 1, participants will be asked to complete short questionnaires daily (e.g., POMS, SAI, Sleep, Stress), which takes about 5-10 minutes. In addition, they will be asked to wear a wristband that monitors their heart rate continuously until the end of the study.

After the Week 1 session, we email participants once asking to provide the details of the medications that they are currently taking (e.g., dosage, uses, ingredients). They will be asked to report any changes in medications on the following lab visits (21.2). During the following lab visits, we will also ask participants safety questions, such as "Did you notice any changes in your health or well-being this past week?" to ensure their safety and well-being throughout the study (21.2). Additionally, we will ask female participants the following questions:

- Did you have a menstrual period since your last visit?
- If so, when was the first day of your period?

Week 2:

In the morning of Week 2 visit, participants will be asked to collect saliva samples at home using provided swabs, which will take a few minutes. Participants will individually visit the lab once, which will take about 3 hours.

First, the participant will be asked to fill out emotion questionnaires (e.g., CESD, STAI), and to provide saliva samples in the lab. The participant will be asked to answer a few questions about an upcoming decision-making task, which will be administered on Week 7 (e.g., If you want to split \$10 between you and someone else, how much money do you offer to the other person?). Additionally, we will assess body measures including height, weight, waist and hip circumferences. This part will take about 20 min.

Second, the participant will practice a computer-based emotion regulation task, which they will be asked to do in a fMRI scanner later on. In this emotion regulation task, participants will see a series of pictures (neutral, emotional from IAPS uploaded to 21.2) while they try to increase, decrease or just feel the emotion elicited by the picture. After each picture, they will be asked to rate the strength of the emotion they are currently feeling. The practice session will take about 20 min.

Third, we will walk the participant over to DNI and put them in a scanner. The participant will complete a computer-based emotion regulation task while their heart rate, breathing, blood pressure, skin conductance, CO₂ levels and pupil size are being recorded. In addition, the participant will undergo structural and functional scans while they rest. This part of the study will take about an hour and 15 min.

Fourth, we will escort the participant back to the lab. The participant will undergo the first HRV training session, which will take up to an hour. The researchers will give step-by-step training instructions to the participants using Lehrer et al.'s protocol (Lehrer et al., 2013). Please note that we will adapt the text to omit discussion of "your symptoms." For example, we will say "control your heart rate" instead of "control your symptoms." Participants in the increase-HRV group will be asked to breathe at a slow and steady

rate that maximally increases HRV (approximately 6 breaths/min). The decrease-HR/HRV group will undergo a similar procedure except that they will be asked to breathe normally. Then, the researcher will work with the participant to practice the assigned exercise using the home biofeedback devices. The researcher will ensure that these breathing manipulations would not cause any discomfort to the participant. Participants will then be asked to use the home biofeedback devices to record their heart rate variability (HRV) during a 5-minute resting period while the researchers assist them and make sure they understand the instructions.

Fifth, participants will be asked to take an olfactory test where they identify 12 different smells (e.g., orange) by choosing one of the four options (e.g., orange, strawberry, blackberry, pineapple).

http://www.usneurologicals.com/index.php?app=ecom&ns=prodshow&ref=ST_SniffinSticks

For the rest of Week 2, participants will be asked to do the assigned practice (increase-HRV or decrease-HR/HRV described above) for 10-20 min twice a day using the home biofeedback devices and record their HRV data.

Week 3:

The same group of participants formed in Week 1 will visit the lab together, once in the beginning of Week 3. This lab visit will take about 2 hours. First, the researchers will download and check their weekly data to make sure that they have completed the assigned task daily. The researcher will work with participants one-on-one to complete the assigned breathing practice using the home biofeedback devices and give them tips to increase HRV or decrease HR/HRV. For instance, the researcher will ask them to try sometimes doing the session with their eyes closed without attending to the feedback until after the session is over, to see if that works better for them. Each participant will be given a target score for the remaining days of Week 3 and will be asked to complete the assigned practice for 10-20 min twice a day using the home biofeedback devices and record their data.

The participants are allowed to talk to each other, share their experience of home practice and exchange tips. The researchers will also share how all the other participants in the same condition are doing (e.g., we will present a chart showing a completion rate of daily assignment of each participant without their identifiable information, and how many extra practices they attempted within a week), and as detailed in the payment section, give everyone an incentive if everyone has completed the target number of practice sessions - this is to encourage participants to carry out training with other participants in this study. Lastly, participants will be asked to complete some questionnaires (e.g., altruism questions) and cognitive tasks.

Weeks 4-5:

Participants will go through a similar procedure as Week 3 and get tips from the researchers regarding best practices for improving the assigned biofeedback exercise. We will also administer memory tests (see below for description). At home, they will be

asked to do the biofeedback exercises up to 20 min twice a day. Each of the weekly lab visits should last about 2 hours.

Memory tests: Participants will be asked to view a series of pictures (i.e., NAPS or IAPS in 21.2) and rate them. Sometime later, participants will be asked to indicate whether they have seen each picture or not (recognition memory test). They will also be asked to recall pictures (recall memory test). A week later when they return to the lab, participants will be asked to indicate whether they have seen each picture or not by pressing the yes or no keys (recognition memory test). They will also be asked to recall stories that they created in the previous week (recall memory test). During the task, their heart rate, breathing and pupil size may be recorded.

Week 6:

The participants will visit the lab as a group. We will record their resting HRV for 5 min using the home devices and repeat measures from Week 1 (i.e., questionnaires, Stroop, PASAT, cognitive and emotion tasks, blood draw). As a group, the participants and researchers will discuss their experience in this study. The participants will be encouraged to share as much or as little as they would like, and the researchers will take any questions or concerns that they have. This lab visit should last about 3 hours.

For the rest of Week 6, they will be asked to continue the assigned practice for up to 20 min twice a day. Participants will also be asked to continue to fill out questionnaires and wear a wristband every day.

Week 7:

In the morning of Week 7 visit, participants will be asked to collect saliva samples at home using provided swabs, which will take a few minutes. Participants will also be asked to visit the lab individually to complete the same assessments as in Week 2. The entire visit (both the lab and MRI sessions) will take about 3 hours. In the MRI session, there will be additional scans including paced-breathing (e.g., 10 sec/breath), training-mimicking and decision-making scans. The training-mimicking scan is where we ask participants to do the biofeedback exercises that they have been practicing at home. During the decision-making scan, the participant will be asked to decide whether to accept or reject monetary offers from other participants in a decision game. At the end, they will be asked about the tasks they completed and their experiences during this study.

References

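### Participants train in same-condition groups of up to 6, but no SAP analysis has a training-group term; a group-adjusted analysis of at least the primary outcome should stand beside the 2×2 ANOVA.

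*Protocol*

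**What the plan says.** **Group structure.** At Week 1, "a group of eligible participants in the same condition (HRV-increase or HR/HRV-decrease, up to 6 people) will be invited to visit the lab". In Week 3, "The same group of participants formed in Week 1 will visit the lab together". Weeks 4-5 follow a similar procedure, and Week 6 is again a group visit.

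**Contact between members.** From Week 3, "The participants are allowed to talk to each other, share their experience of home practice and exchange tips". Researchers show an anonymised chart of each participant's completion rate and, "as detailed in the payment section, give everyone an incentive if everyone has completed the target number of practice sessions". The payment section is not among the documents.

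**Individual elements.** For Week 2, "Participants will individually visit the lab once, which will take about 3 hours"; that visit includes the baseline scan and the first training session. The Week 7 scan visit is also individual. Week 3 practice is coached one-on-one, and daily practice is done at home. At Week 1, "3-5 researchers will conduct this group session", so a group does not correspond to one trainer.

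**Analysis.** SAP section 5 tests the primary outcome, right amygdala-mPFC connectivity, with a time × condition mixed ANOVA. The remaining analyses are two- and three-way ANOVAs, Mann-Whitney tests, t-tests, and weekly mixed models with a random participant intercept. None has a training-group term. SAP section 2 makes no allowance for clustering.

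**Allocation.** Neither document states the unit of allocation. SAP section 4 refers to randomization subjects, which reads most naturally as individuals. The protocol points to a separate publication for more detail.

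**The concern.** Each training group lies wholly within one condition, so anything that makes its members change alike adds to the variance of the difference between conditions. An analysis that treats participants as independent leaves that variance out. Its standard errors are then too small and its p-values too low.

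The protocol creates routes for such correlation: shared tips, visible completion rates, and an incentive that depends on every member. These act on practice, which is the dose of the intervention. Individual allocation would not remove them, because the dependence can arise after allocation.

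Exposure differs by outcome:

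- **Primary outcome:** scanned individually, so probably least affected, though not exempt from correlation through practice.
- **Stress tasks, cognition and blood markers:** taken at the Week 1 group visit and again at Week 6, which is to "repeat measures from Week 1 (i.e., questionnaires, Stroop, PASAT, cognitive and emotion tasks, blood draw"). These may be more exposed.
- **Mood:** unclear. POMS and SAI are also among the daily questionnaires, CES-D and STAI are also completed at individual visits, and the SAP does not say which administration counts as pre or post.

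**Working it through.** **Inputs from the documents.** Group size up to 6, one condition per group (Protocol, Week 1). α = .05, f = .25, correlation .5, planned N = 46 for 90% power (SAP section 2). Participants: 121 younger + 72 older = 193 (SAP section 2), before exclusions.

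**Assumed, because the documents are silent.** ICC of change 0 to 0.10; actual group sizes; whether groups mixed ages.

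**1. The plan's own figure.** For the within-between interaction, λ = f²·N·2/(1 − .5) = 0.0625 × N × 4 = 0.25N. With N = 46, λ = 11.5 on 1 and 44 df, and power is 0.912. N = 44 gives 0.8997, so 46 is the smallest even N reaching 90%. The figure reproduces, for independent participants. Setting 0.25N equal to d²N/4 gives d = 1.0: the planned effect is a between-condition difference of 1.0 SD of change.

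**2. Type I error of the unadjusted test.** With m members per group, DE = 1 + (m − 1)·ICC, and the true error is 2·(1 − Φ(1.96/√DE)). Example: m = 6, ICC 0.10 gives DE = 1.5, 1.96/√1.5 = 1.60, error 11.0%.

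| Members per group | ICC 0 | 0.01 | 0.05 | 0.10 |
|---|---|---|---|---|
| 6 (the maximum) | 5.0% | 5.6% | 8.0% | 11.0% |
| 4 | 5.0% | 5.3% | 6.8% | 8.6% |
| 3 (e.g. mixed-age groups analysed by age) | 5.0% | 5.2% | 6.2% | 7.4% |

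**3. Which results would change.** The nominal p needed to stay below 0.05 after adjustment is 2·(1 − Φ(1.96·√DE)). For groups of 6 it is 0.0446, 0.0284 and 0.0164 at ICC 0.01, 0.05 and 0.10. A nominal p between the threshold and 0.05 would lose significance.

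**4. Simulation check.** Change scores with equal arms, 40,000 replicates, ICC 0 / 0.01 / 0.05 / 0.10. The unadjusted test rejected a true null in 5.1 / 5.7 / 8.0 / 10.8% of runs with 12 groups of 6, and 4.8 / 5.1 / 6.8 / 8.7% with 48 groups of 4. A t-test on group means stayed at 4.7-5.2% in all equal-size settings. With uneven groups of 2-6 and N = 72 (10,000 replicates, ICC 0 / 0.05 / 0.10), the unadjusted test gave 5.0 / 6.6 / 9.0%; group means stayed at 4.4-5.2%.

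**5. Power after adjustment.** Noncentral t with ncp = d·√N/(2·√DE), at DE = 1.5. Group df = number of groups − 2, assuming full groups of 6 (12, 20 and 32 groups). N = 72 and N = 121 also assume groups separated by age.

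| Difference in change | N | Unadjusted | DE 1.5, N − 2 df | DE 1.5, group df |
|---|---|---|---|---|
| 1.0 SD (SAP's f = .25) | 72 | 0.99 | 0.93 | 0.88 |
| 0.5 SD (assumed) | 72 | 0.55 | 0.40 | 0.35 |
| 0.5 SD (assumed) | 121 | 0.78 | 0.61 | about 0.56 |
| 0.5 SD (assumed) | 193 | 0.93 | 0.81 | 0.78 |

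Even at ICC 0 the group-mean test costs power at 0.5 SD: from 0.55 to 0.48 with 12 groups, and from 0.93 to 0.92 with 32.

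**The case against.** The strongest reply is that no error has been shown. Every rate above 5% comes from an assumed ICC, and the documents give no basis for choosing one. The 11.0% needs full groups of 6 and an ICC of 0.10 together; six is a ceiling, and restriction to completers with usable data makes analysed groups smaller. A stable difference between groups cancels in the time × condition contrast, so only a group effect on change matters, and measurement at a group visit does not by itself create one. The primary outcome, where the fix is asked for first, is the one with the most individual contact: individual scans, an individual first training session, one-on-one coaching and home practice.

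The remedy also has limits. In 20,000 simulated trials with groups of 6 and a true ICC of 0.05, the estimated ICC was zero or negative in 33% with 12 groups, 26% with 20 and 19% with 32. With 12 groups its 5th to 95th percentile range was about −0.09 to 0.21. A reported ICC near zero would not clear the concern.

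All of this stands as a limit on size, and it is why the adjusted analysis belongs beside the ANOVA. It does not remove the point. The protocol sets up influence between members on practice, independence is assumed without a check, and the group-mean test holds its level without relying on a precise ICC. The primary outcome comes first because it carries the trial's main claim.

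**Conclusion.** The concern holds. Training groups are nested in condition, and no analysis or sample-size statement allows for it. This is an unchecked independence assumption, not a demonstrated false result. If change is positively correlated within groups, a nominal 5% test has a true error of 5.2% to 11.0% over assumed ICCs of 0.01 to 0.10 and groups of 3 to 6; at ICC 0 there is no harm. The main risk is type I error and intervals that are too narrow, most relevant to results with nominal p between about 0.016 and 0.05. The conclusion rests on unknown ICCs and group sizes and on an unstated unit of allocation, so confidence is medium. It should be fixed, because the check is cheap.

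**What to change.** - State whether individuals or whole groups were allocated, and give the number and sizes of training groups by condition and age group.
- Report the ICC of pre-post change with its uncertainty; a low estimate from few groups is not reassurance.
- Beside the 2×2 ANOVA of the primary outcome, report one group-adjusted analysis: a random training-group effect on change with small-sample degrees of freedom, or a t-test on group means when groups are few.
- Preferably do the same for outcomes measured at the Week 1 and Week 6 group visits, and state which mood administrations are pre and post.
- If individuals were allocated, this can be a sensitivity analysis. If whole groups were allocated, it should be the main analysis.

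**Cost.** Some reanalysis, since the SAP describes completed analyses, but no new outcome data. Group membership must be retrievable, which the documents do not confirm. Intervals widen and power falls as tabulated above, with some loss even when the ICC is zero; hence the planned ANOVA should be kept alongside unless whole groups were allocated.

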Statistical Analysis Plan (SAP)

Principal Investigator	[name] Professor of Gerontology, Psychology and Biomedical Engineering University of Southern California Los Angeles, California, USA
Protocol identification number	UP-17-00219
ClinicalTrials.gov identifier	NCT03458910
Author	[name] Research Associate [name] of Southern California Los Angeles, California, USA
Version	Draft 0.2
Date	09/09/2024

1. Objectives and hypotheses

The main objective of the study was to test the hypothesis that daily biofeedback sessions stimulating heart rate oscillatory activity in baroreflex frequencies affect the function of brain networks involved in emotion regulation. Our main outcome measure was pre-to-post intervention changes in resting-state right amygdala functional connectivity with a medial prefrontal cortex region associated with heart rate variability (HRV). Our secondary outcome measures were pre-to-post intervention changes in up- and down-regulation of amygdala activity and self-reported emotion regulation effectiveness during viewing emotional pictures, as well as changes in ratings of emotional well-being. Other secondary outcome measures included HRV during rest, measures of cerebral blood flow, decision making, stress responsivity and cognitive performance. As a post-hoc outcome measure, we examined pre-to-post intervention changes in resting-state left amygdala functional connectivity with a medial prefrontal cortex region.

2. Sample Size & Power consideration

121 younger adults and 72 older adults participated in the study.

No prior studies had examined effects of these interventions on brain function so we were unable to estimate effect sizes based on prior neuroimaging data. We elected to power our study to detect medium or larger effect sizes. Our main planned statistical comparisons were repeated-measures ANOVAs with within-between interactions. For these, a total sample size of 46 would give 90% power to detect moderate effect sizes of $f=.25$ with $\alpha = .05$, given an assumed correlation among the repeated measures of .5 (Faul et al., 2007). We also planned to examine within-subject change within each of the conditions. A sample size of 44 in each condition (HRV-increase, HRV-decrease) would give 90% power to detect within-group change effect sizes of $d=.5$ in a two-tailed t-test with $\alpha = .05$ (Faul et al., 2007). Thus, we aimed for an N=200 completion rate across the two conditions and two age groups to be able to accommodate potential exclusions for movement during imaging or other data quality issues. Due to the COVID-19 pandemic leading to increased risk for participants completing lab visits, we terminated the study before achieving our initial goal of recruiting 100 older participants.

3. Outcomes

For most outcome measures, we examined group difference (HRV-increase vs. HRV-decrease) in pre-post intervention change. The average time between pre and post intervention assessment was 5 weeks.

Primary outcome measures

- Group difference in pre-post intervention change in resting state functional connectivity between the right amygdala and medial prefrontal cortex (mPFC)

Secondary outcome measures

- Group difference in pre-post intervention change in:
 - Emotion regulation ability measured by self-reported effectiveness when instructed to regulate emotion during viewing emotional pictures
 - The ability to up- and down-regulate amygdala activity when instructed to regulate emotion during viewing emotional pictures
 - Emotional well-being measured by the Profile of Mood States (POMS), the State Anxiety Inventory (SAI), the Trait Anxiety Inventory (TAI) and the Center for Epidemiologic Studies (CES-D)
 - HRV measured by high frequency power (HF)
 - HRV measured by low frequency power (LF)
 - HRV measured by the root mean square of successive differences (RMSSD)
 - Inflammatory markers including C-reactive protein, IL-1b, IL-6, IL-8 and TNF-a
 - Stress recovery
 - Stress reactivity
- Group difference in cerebral blood flow during pre-intervention resting state and post-intervention paced-breathing
- Group difference in decision-making ability measured by multiple-choice responses during a computer-based decision-making task at the post-intervention MRI
- Group difference in the ability to up- and down-regulate task-relevant brain regions during a computer-based decision-making task at the post-intervention MRI

Other outcome measures

- Group difference in pre-post intervention change in:
 - Working memory measured by NIH Toolbox List Sorting Working Memory Test (LSWM)
 - Processing speed measured by NIH Toolbox Pattern Comparison Processing Speed Test (PCPS)
 - Inhibitory control and attention measured by NIH Toolbox Flanker Inhibitory Control and Attention Test (Flanker)
 - Sustained attention measured by Sustained Attention to Response Test (SART)
 - Stress measured by cortisol levels
- Group difference in recognition memory after about three and half weeks of training
- Group difference in recall memory after about three and half weeks of training

Safety outcomes

No adverse events were observed.

4. Populations and subgroups to be analyzed

Population analyzed is composed by all randomization subjects who completed assessments and whose data quality was sufficient for data analysis.

5. Analyses

Primary outcome measures

- Resting state functional connectivity between the right amygdala and medial prefrontal cortex (mPFC): We performed a 2 (time point: pre, post) \times 2 (condition: HRV-increase, HRV-decrease) mixed ANOVA. The effect of interest was a time \times condition interaction, and P values less than 0.05 were considered statistically significant.

Secondary outcome measures

- Emotion regulation (behavioral analysis):
We conducted a three-way ANOVA to examine whether emotional intensity rated by participants during emotion regulation changed after HRV biofeedback intervention for younger and older adults separately. The 2 \times 2 \times 3 ANOVA model included three factors: time-point (2 levels: pre- and post-intervention), intervention condition (2 levels: HRV-Increase, HRV-Decrease) and regulation type (3 levels: down-regulation, viewing and up-regulation). P values less than 0.05 were considered statistically significant.
- Emotion regulation (MRI analysis):
We conducted a three-way ANOVA to examine whether BOLD activity in the left and right amygdala changed during emotion regulation after HRV biofeedback intervention for younger and older adults. The 2 \times 2 \times 3 ANOVA model for each amygdala included three factors: time-point (2 levels: pre- and post-intervention), intervention condition (2 levels: HRV-Increase, HRV-Decrease) and regulation type (3 levels: down-regulation, viewing and up-regulation). P values less than 0.05 were considered statistically significant.
- Emotional well-being (pre/post):
To test whether emotional well-being changed during the course of the study and whether this depended on training condition, we performed a series of two-way mixed ANOVAs, one for each measure. In these ANOVAs, time was a within-subjects factor (2 levels: pre- and post-intervention) and condition was a between-subjects factor (2 levels: HRV-Increase, HRV-Decrease). For each ANOVA, the effect of interest was a time \times condition interaction, and only data from participants with values for both time points were included. P values less than 0.05 were considered statistically significant. ANOVAs were performed with R (Version 4.0.3) and the R package 'ez'.
- Emotional well-being (all weeks):
To test whether emotional well-being changed during the course of the study and whether this depended on training condition, we fit a series of linear mixed effects models, one for each measure. For these models, fixed effects were time (1 level per week), condition (2 levels: HRV-Increase, HRV-Decrease), and a time \times condition interaction. The models included random intercepts for participants. For each model, data from all available participants at each time point was used. To assess parameter significance, F- and p-values were determined using Satterthwaite's method. P values less than 0.05 were considered statistically significant. These

analyses were performed with R (Version 4.0.3) and the R packages 'lmer4' and 'lmerTest'.

- HRV measured by high frequency (HF) HRV, low frequency (LF) HRV and the root mean square of successive differences (RMSSD):
To test whether HRV changed during the course of the study and whether this depended on training condition, we performed a series of two-way mixed ANOVAs, one for each measure. In these ANOVAs, time was a within-subjects factor (2 levels: pre- and post-intervention) and condition was a between-subjects factor (2 levels: HRV-Increase, HRV-Decrease). For each ANOVA, the effect of interest was a time x condition interaction, and only data from participants with values for both time points were included. P values less than 0.05 were considered statistically significant. ANOVAs were performed with IBM SPSS statistics (Version 27) and R (Version 4.0.3) with R package 'ez'.
- Inflammatory markers:
For each inflammatory marker (IL-1b, IL-6, IL-8, TNF-a, CRP), we conducted a two-way ANOVA to examine whether its levels changed after HRV biofeedback intervention for younger and older adults separately. The 2 x 2 ANOVA model included two factors: time-point (2 levels: pre- and post-intervention) and intervention condition (2 levels: HRV-Increase, HRV-Decrease). P values less than 0.05 were considered statistically significant.
- Recovery from stress:
To test whether stress recovery changed during the course of the study and whether this depended on training condition, we performed a series of two-way mixed ANOVAs, one for each measure of stress recovery. In these ANOVAs, time was a within-subjects factor (2 levels: pre- and post-intervention) and condition was a between-subjects factor (2 levels: HRV-Increase, HRV-Decrease). For each ANOVA, the effect of interest was a time x condition interaction, and only data from participants with values for both time points were included. P values less than 0.05 were considered statistically significant. ANOVAs were performed with R (Version 4.0.3) and the R package 'ez'.
- Reactivity to stress:
To test whether stress reactivity changed during the course of the study and whether this depended on training condition, we performed a series of two-way mixed ANOVAs, one for each measure of stress reactivity. In these ANOVAs, time was a within-subjects factor (2 levels: pre- and post-intervention) and condition was a between-subjects factor (2 levels: HRV-Increase, HRV-Decrease). For each ANOVA, the effect of interest was a time x condition interaction, and only data from participants with values for both time points were included. P values less than 0.05 were considered statistically significant. ANOVAs were performed with R (Version 4.0.3) and the R package 'ez'.
- Cerebral blood flow measured by Arterial Spin Labeling (ASL):

We conducted a two-way ANOVA to examine whether whole-brain cerebral blood flow, as measured by arterial spin labeling MRI, changed over the course of the study as a result of training condition. Specifically, we examined cerebral blood flow at rest at the beginning of the study (i.e., before any intervention) and we examined cerebral blood flow during paced breathing at study completion (i.e., at the end of 5-week training). A 2x2 ANOVA was modeled with time as a within-subjects factor (2 levels: pre- and post-intervention) and training condition as a between-subjects factor (2 levels: HRV-Increase, HRV-Decrease). The effect of interest was the time x training condition interaction. Only participants with usable arterial spin labeling MRI scans at both time points were included in analyses. P values less than 0.05 were considered statistically significant. Statistical analyses were performed in IBM SPSS Statistics version 27.

- Decision-making (behavioral analysis):
To compare the response to unfair and fair offers between groups, we conducted two Mann-Whitney tests. In these analyses, acceptance rates for unfair and fair offers were dependent variables and group (HRV-Increase vs. HRV-Decrease) was defined as between subject independent variable. P values less than 0.05 were considered statistically significant.
- Decision-making (MRI analysis):
We conducted two independent t-test analyses to examine whether BOLD activity in the dorsal anterior cingulate cortex and anterior insula in response to linear effect of unfairness differs between group. Linear effect of unfairness was defined using a linear regression with offer values as independent variable and brain activity as the dependent variable. P values less than 0.05 were considered statistically significant.

Other outcome measures

- Cognition (Working memory, Processing Speed, Inhibitory Control and Attention):
To test whether cognitive function changed during the course of the study and whether this depended on training condition, we performed a series of two-way mixed ANOVAs, one for each measure. In these ANOVAs, time was a within-subjects factor (2 levels: pre- and post-intervention) and condition was a between-subjects factor (2 levels: HRV-Increase, HRV-Decrease). For each ANOVA, the effect of interest was a time x condition interaction, and only data from participants with values for both time points were included. P values less than 0.05 were considered statistically significant. ANOVAs were performed with IBM SPSS statistics (Version 27).
- Sustained Attention to Response Task (SART):
We conducted a three-way ANOVA to examine whether number of errors during the SART task changed after HRV biofeedback intervention for younger and older adults separately. The 2 x 2 x 2 ANOVA model included three factors: time-point (2 levels: (pre- and post-intervention), intervention condition (2 levels: HRV-Increase, HRV-Decrease), and error type (2 levels: commission error and omission error). The commission error occurs when participants pressed a button in trials where they are not supposed to press it. The omission error occurs when participants did not

press the button in trials where they are supposed to press it. P values less than 0.05 were considered statistically significant.

- Stress measured by cortisol levels at awakening and 30 min later: We conducted a three-way ANOVA to examine whether cortisol levels at awakening and 30 min later changed after HRV biofeedback intervention for younger adults. The $2 \times 2 \times 2$ ANOVA model included three factors: time-point (2 levels: (pre- and post-intervention), intervention condition (2 levels: HRV-increase, HRV-decrease), and cortisol collection timing (2 levels: cortisol at awakening and 30 min later). P values less than 0.05 were considered statistically significant. To reduce participant burden for older adults, we did not collect saliva samples from them so could not assess this measure for them.
- Recognition memory: We conducted a two-way ANOVA on recognition memory measures to determine if emotional memory differed between conditions as a result of the HRV biofeedback intervention for younger and older adults separately. In the 3×2 ANOVA, valence was a within-subjects factor (3 levels: neutral, positive, negative) and condition was a between-subjects factor (2 levels: HRV-Increase, HRV-Decrease). P values less than 0.05 were considered statistically significant.
- Recall memory: We conducted a two-way ANOVA on free recall memory to determine if emotional memory differed between conditions as a result of the HRV biofeedback intervention for younger and older adults separately. In the 2×2 ANOVA, valence was a within-subjects factor (2 levels: positive, negative) and condition was a between-subjects factor (2 levels: HRV-Increase, HRV-Decrease). P values less than 0.05 were considered statistically significant.
